## 5.0 Multiple sites:

N/A

## 6.0 Incomplete Disclosure or Deception:

N/A

## 7.0 Recruitment:

Participants will be recruited from the Departments of Internal Medicine, Pulmonary Medicine, and Family Medicine at Rush University Medical Center. We will post study recruitment materials in each clinic, and will ask providers to refer interested and potentially eligible patients to the study team. We will also create an audio hold recording to be played on the Rush on-hold line. Potential participants will be asked to call the

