**Participants.**

[figure not shown]
The randomized factorial experiment will consist of 48 participants. We will partner with the American Lung Association (ALA) Illinois chapter team and recruit participants from the ALA COPD Helpline for this study, following recruitment procedures described below. The PI has collaborated with the ALA-Illinois chapter team since 2015, and the proposed research is a natural extension of this partnership. As the ALA Living Well with COPD programs reaches over 800 callers per year, we believe that accrual targets (4 participants/ month; planned N=48) will be feasible in the grant period.

**Procedures.** We will conduct a pilot randomized factorial trial in which participants will be randomized to one of two levels for each of the four intervention components. This will result in a total of 16 study conditions, 3 participants per condition (N=48).

**Length of participation.** As shown in Figure 4, participants will be enrolled in the study for approximately 4 months (14 weeks).

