**Figure 3. Study Procedures**

**Figure 4. Study Schedule for Each Treatment Condition**

## PROTOCOL TITLE: COPD Helpline study

Within multi-component programs, treatment components targeting physical activity are uniquely associated with improved health-related quality of life. Additionally, provision of social support is a critical component of COPD self-management treatment. Receiving positive social support from caregivers is consistently associated with improved health-related quality of life and self-efficacy among individuals with COPD. Overall, the four intervention components to be tested in the current study are supported by rigorous scientific evidence, relevant to a range of COPD stages, and can be combined with no conflict or redundancy in an optimized self-management intervention.

Self-management education duration (short vs. long). The self-management education condition is based on the Living Well with COPD program, which has been researched extensively. The program consists of a mailed booklet and structured phone counseling delivered by certified COPD educators. Topics include disease information, breathing retraining, action planning, medication use, energy conservation, and following good health habits. The ALA has offered the Living Well with COPD program to over 5700 callers with COPD since 2016.

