## PROTOCOL TITLE: COPD Helpline study

ALA Lung Helpline and ask about the ‘Rush COPD Management study;’ they may also choose to provide their contact information to receive a phone call from an ALA Lung Helpline counselor.

Study recruitment will be supplemented by partnerships with Rush University organizations such as the Tobacco Oversight Committee and Lung Cancer Screening Program, and community partners who serve individuals with COPD, including the American Lung Association, Respiratory Health Association, and local COPD support groups and Pulmonary Rehabilitation programs. [name] will share IRB-approved recruitment materials with community partners through multiple communication channels (i.e., community events, newsletters, e-newsletters, website postings, tweets) to reach potentially eligible individuals with COPD. We will also advertise our study and recruit participants through Researchmatch.org, a nonprofit program funded by the National Institutes of Health (NIH) that allows researchers to connect with people interested in research studies.

All study procedures are conducted remotely, precluding any cost or burden associated with travel to the research center. The ALA Helpline counselors will provide a brief study description and assess the caller’s interest in participating at the time of their initial telephone intake. They will share contact information of interested callers through a brief REDCap form. Interested callers will be contacted by the research team for a full study description and eligibility screening. If eligible, callers will complete informed consent remotely via a secure REDCap link sent by text message or email, and will be randomized to treatment.

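### Does Section 7.0, which opens with Rush departments, contradict the Helpline source and accrual basis in Section 4.0?

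*Combined protocol and SAP*

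**What the plan says.** Section 4.0 (Participants) says the team will "recruit participants from the ALA COPD Helpline for this study, following recruitment procedures described below". Its only support for the accrual target is the volume of the ALA's Living Well with COPD offering: "programs reaches over 800 callers per year, we believe that accrual targets (4 participants/ month; planned N=48) will be feasible in the grant period". The other volume in the protocol, in the description of the education component, is for the same program: "The ALA has offered the Living Well with COPD program to over 5700 callers with COPD since 2016". Section 4.0 (Pre-Screening and Baseline Assessment) also puts ALA counselors first in the recruitment sequence, before research staff make contact.

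Section 7.0 begins: "Participants will be recruited from the Departments of Internal Medicine, Pulmonary Medicine, and Family Medicine at Rush University Medical Center". Clinics will display study materials, a recording will play on the Rush hold line, and the team "will ask providers to refer interested and potentially eligible patients to the study team". Potential participants are then asked to telephone the ALA Lung Helpline and name the study, or to leave details so that a counselor can call them. The next paragraph reads: "Study recruitment will be supplemented by partnerships with Rush University organizations such as the Tobacco Oversight Committee and Lung Cancer Screening Program", and adds "community partners who serve individuals with COPD, including the American Lung Association, Respiratory Health Association, and local COPD support groups and Pulmonary Rehabilitation programs". An online research-matching service is a further source. A separate paragraph has Helpline counselors describe the study and gauge callers' interest "in participating at the time of their initial telephone intake".

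Recruitment rate is one of the quantities Aim 2 (Section 1.0) is meant to deliver for the later optimization trial. Section 4.0 (Analytic Strategy) lists enrollment ratios and monthly recruitment rates among the feasibility measures.

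**The concern.** On a first reading the two sections name different main sources. One rests the target entirely on people the ALA program already reaches. The other puts three hospital departments first and mentions the ALA in a sentence about supplementary partners. A patient who sees a poster at Rush and rings the Helpline because of it is not one of the 800 ordinary callers, even though the call arrives on the same line. The documents give no volume for Rush or for any other added source.

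The provider route also looks unsettled. Providers send patients to the study team, while elsewhere a Helpline counselor comes first.

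The stake would be the meaning of a main feasibility result. A pooled monthly rate does not by itself show how many ordinary Helpline callers enroll, and an enrollment ratio depends on who is in its denominator. If the optimization trial drew on a different mix of sources, the pilot rate might not carry over.

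**Working it through.** **The plan's own figures.** Inputs, all from Section 4.0: four two-level factors, 3 participants per condition, 4 participants a month, over 800 callers a year.

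- Sample size: 2^4 = 16 conditions; 16 × 3 = 48. This reproduces N=48.
- Accrual time: 48 / 4 = 12 months.
- Callers per month: 800 / 12 = 66.7.
- Implied yield: 4 / 66.7 = 48 / 800 = 6.0% of callers. The text says over 800, so this is an upper bound.

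The figure of over 5700 callers since 2016 has no end date, so no yearly volume can be derived from it without an assumption. It is not used here.

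**What added sources do to the target.** Let s be the share of the 48 who are ordinary Helpline callers. The documents do not give s, so the values below are assumptions that span the whole range. Yield needed = 48s / 800; other sources must supply 4(1 − s) a month.

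| s (assumed) | Ordinary callers enrolled | Yield needed | From other sources, per month |
|---|---|---|---|
| 100% | 48 | 6.0% | 0 |
| 75% | 36 | 4.5% | 1 |
| 50% | 24 | 3.0% | 2 |
| 25% | 12 | 1.5% | 3 |
| 0% | 0 | 0% | 4 |

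The pooled rate is 4.0 a month in every row. Section 4.0 in effect argues the top row, which asks most of the Helpline. Leaving the other sources out of that argument does not make the target look easier for the Helpline than it is.

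**The text side by side.**

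1. *Source.* The sentence in Section 4.0 that names the Helpline refers the reader to procedures given later, and Section 7.0 is where they are given. Section 7.0 directs people reached through Rush publicity to the Helpline, by their own call or a counselor's. The point of entry therefore agrees with both parts of Section 4.0.
2. *Role of the ALA.* In the sentence on supplementary sources the ALA appears as a community partner, and the sentence that follows says such partners circulate approved materials. Counselor intake has its own paragraph and is not called supplementary. The ALA has two roles, and listing one does not demote the other.
3. *Provider referrals.* Referral to the study team and a later Helpline call can be consecutive steps. The text does not say that they are, but nothing in it makes them exclusive.
4. *Analysis.* Enrollment ratios and monthly rates are planned with no limit on how they are broken down. A table by referral source fits within that plan wherever source has been noted.

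**The case for a change.** The strongest case for a change is that a shared entry channel is not a shared source population. The 800 figure describes existing callers, whereas Section 7.0 sets out to create new ones. Since the study concerns treatment delivered through the Helpline, yield among ordinary callers is a natural planning quantity. The table shows that one pooled rate is compatible with very different values of it. Source is also easier to record at first contact than to reconstruct later, and the documents do not show whether the intake form captures it.

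Part of this stands. The accrual paragraph does omit the added sources, the protocol gives no volume for them, and it does not say whether provider referrals also pass through Helpline intake. A source field would be good practice.

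It does not amount to a defect in the plan. The harm depends on the later trial using a different mix, which the documents do not say. The splits are assumptions and give no evidence that the Helpline basis fails. Yield per caller offered the study would also cost more than one field: Section 7.0 has counselors pass on only the interested callers, so they would have to start logging those who decline. Asking for the study by name is only a partial marker, because people called back by a counselor or referred by a provider need not name it.

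**Conclusion.** The mismatch in wording is real, but it is a matter of drafting. Sections 4.0 and 7.0 can be followed together as one recruitment funnel. N=48 and the 12-month accrual period reproduce. The implied yield of at most 6.0% of a year's callers is a ceiling that falls with every recruit from elsewhere. The recruitment rate will be a valid estimate for the mix of sources the protocol describes, and analysts can describe it by source within the measures already planned.

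This conclusion assumes that Section 7.0 is the set of procedures to which Section 4.0 refers, and that enrollment is open for about 12 months at the stated pace. It does not establish that 4 a month will be reached, because the documents give no observed yield for any source. The two paragraphs could be aligned whenever the protocol is next edited, but no result depends on it, so no change to the plan is called for.

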## PROTOCOL TITLE: COPD Helpline study

ALA Lung Helpline and ask about the ‘Rush COPD Management study;’ they may also choose to provide their contact information to receive a phone call from an ALA Lung Helpline counselor.

Study recruitment will be supplemented by partnerships with Rush University organizations such as the Tobacco Oversight Committee and Lung Cancer Screening Program, and community partners who serve individuals with COPD, including the American Lung Association, Respiratory Health Association, and local COPD support groups and Pulmonary Rehabilitation programs. [name] will share IRB-approved recruitment materials with community partners through multiple communication channels (i.e., community events, newsletters, e-newsletters, website postings, tweets) to reach potentially eligible individuals with COPD. We will also advertise our study and recruit participants through Researchmatch.org, a nonprofit program funded by the National Institutes of Health (NIH) that allows researchers to connect with people interested in research studies.

All study procedures are conducted remotely, precluding any cost or burden associated with travel to the research center. The ALA Helpline counselors will provide a brief study description and assess the caller’s interest in participating at the time of their initial telephone intake. They will share contact information of interested callers through a brief REDCap form. Interested callers will be contacted by the research team for a full study description and eligibility screening. If eligible, callers will complete informed consent remotely via a secure REDCap link sent by text message or email, and will be randomized to treatment.

## 8.0 Consent Process:

Trained study staff members will obtain electronic consent via REDCap following standardized procedures. Specifically, after completing the phone screener, those who remain interested and eligible for the study will be immediately emailed or texted a link to the appropriate IRB-approved online consent form in REDCap. Study staff will discuss the consent form while on the phone with the participant following the screening process. If the participant does not have time for this discussion, a second phone call will be arranged. Individuals who remain interested will provide an online signature on the REDCap consent form. We will attempt to conduct the signature process in one continuous session with the participant. If this is not possible (e.g., the participant uses a cell phone as their only connected device, and is unable to simultaneously talk on the phone and view the REDCap e-consent), study staff will follow the consent process below to obtain verbal consent. Study staff will then follow up with the participant by email/ text to obtain an electronically signed copy of the consent form as soon as possible after the phone call has ended.

Consenting procedures will follow Rush IRB guidance for the use of electronic informed consent to ensure best practices are followed in remotely obtaining informed consent. Study staff will first verify that: 1) the form the participant received is the currently approved version, 2) all pages of the consent were received, and 3) the participant can read all pages of the consent. Study staff will verify the identity of the participant by asking their date of birth. Study staff will then review all information in the consent form, similarly to how this discussion would be conducted in an in-person format. Participants will be provided with ample time to review the consent and ask any questions they may have. Those who remain interested will provide an online signature on the REDCap consent form. A PDF version of the consents will be saved on the secure network drive and emailed or texted to the participant. Informed consent will be obtained prior to any data collection or study procedures. There is no waiting period between informing the prospective subject of their eligibility and obtaining the consent. Non-English speaking individuals, individuals under the age of 18, cognitively-impaired adults, and adults unable to consent will not be included in the current study.

## 9.0 Process to Document Consent:

## PROTOCOL TITLE: COPD Helpline study

Documentation of the consent process will occur within the REDCap e-consent project (i.e., eConsent form with electronic signature for each study participant, Consent Collection Form, and Consent Process Documentation Form).

### 10.0 Risks to Participants:

This is a minimal risk study. Study procedures do not involve any medical procedures or medication use; participants will be informed that this is a non-medical study and will not involve any changes to their usual medical care. All study procedures are conducted remotely, precluding any risks associated with in-person study visits. Potential risks include psychological distress and loss of confidentiality. First, participants will be asked to report on their COPD symptoms, health habits such as cigarette smoking and physical activity, and adjustment to disease/ quality of life. As a result, they may experience discomfort or distress from providing self-report of private, potentially embarrassing information. Second, while we will make every effort to protect privacy and keep data confidential, a risk for loss of confidentiality also exists.

Potential study participants will be informed regarding alternative treatments, including the ALA COPD Helpline, which remains available to callers who opt out of the research study. Callers who are ineligible or choose not to participate will be referred back to the ongoing ALA COPD Helpline and Tobacco Quitline services.

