Novel experimental approaches could help to address this critical research gap and optimize the effectiveness of multi-component COPD self-management interventions on health-related quality of life. The Multiphase Optimization Strategy (MOST) framework is an innovative, engineering-inspired methodological framework for intervention development (Figure 1) that uses highly efficient randomized experimentation to assess the performance of individual intervention components and their interactions on clinically-relevant outcomes. The MOST framework can be used to systematically identify the most promising intervention components, and interactions of components, that drive the effect of self-management treatment on COPD outcomes. The MOST framework can also identify any treatment component, or combination of components, with unintended harmful effects (i.e., inappropriate management strategies for an exacerbation), so that these components can be eliminated from future treatment programs. Thus, MOST is ideally suited to address the significant clinical problem of heterogeneity among self-management programs, and has strong potential to advance the field of self-management treatment for COPD. In the proposed project, we seek to establish the feasibility of using the MOST framework to optimize treatment delivered by the American Lung Association (ALA) Helpline.

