The duration/ intensity of self-management education programs within the research literature is highly heterogeneous, ranging from a single session to 12 or more treatment contacts over up to 24 months. Although one meta-analysis found longer treatment duration to predict lower hospitalization risk, low-intensity treatments have demonstrated clinically significant effects on health-related quality of life and reduced hospitalization. Highly intensive treatment programs may also result in substantial treatment burden for individuals with COPD and limited scalability for population health. Thus, identifying optimal parameters of treatment intensity is critical. We will test a 2-session (short) versus 5-session (long) version of the self-management education program, in combination with the mailed booklet. The short condition consists of two calls (30-45 minutes each) to introduce patient education topics and refer to the booklet for further information. The long condition consists of five, weekly calls (30-45 minutes each) following a structured curriculum of patient education topics.

Ground-based walking training (GBWT; on vs. off). GBWT is a well-established, safe, and feasible physical activity program in COPD. As walking is the most common form of exercise undertaken in daily life, this modality allows for light to moderate intensity physical activity without the need for specialized equipment or professional supervision. Although long-term results are mixed, GBWT is associated with increased daily step count, exercise capacity, and quality of life and at 2- to 3-months. Participants randomized to this condition will be mailed a pedometer (3DFitBud Simple Step Counter) and instructed on its use to establish baseline steps/ day for 7 days. They will then receive a booklet with instructions to establish a walking program and three brief (10-15 minute), bi-weekly calls from a trained staff member to review step count values and engage in setting personal activity goals over the course of 6 weeks, following established exercise guidelines for individuals with COPD. Sessions will be conducted by phone or videoconference via a Zoom meeting hosted on a secure, HIPAA-compliant Rush Zoom account.

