### Monitoring of Safety Data

Overall framework. The PI is responsible for safety oversight, in coordination with an independent safety officer with relevant expertise in this clinical population (i.e., individuals with COPD). The PI will ensure the study is conducted according to the approved protocol. She will ensure all study staff have completed Collaborative Institutional Training Initiative (CITI) and Good Clinical Practice training, as required by the IRB, and are thoroughly trained on study procedures. The PI will develop standardized procedures for identifying, reviewing, and reporting adverse events (including serious adverse events) and unanticipated problems to the independent safety officer, Rush University IRB, and the appropriate offices at NHLBI, as noted in Table 4.

Adverse events. Adverse events are defined as any untoward or unfavorable medical occurrence in a human subject, including any abnormal sign (e.g., abnormal physical exam or laboratory finding), symptom, or disease, temporally associated with the subject's participation in the research, whether or not considered related to the subject's participation in the research. During protocol-designated study contacts, which occur at mid-treatment, end-of-treatment, and 90-day follow-up, research staff will ask participants to report all adverse events that have occurred since the previous study contact. However, participants will be advised to report any adverse event to research staff at any time. Adverse events to be assessed include COPD exacerbation, defined as an acute worsening of symptoms of COPD requiring new or increased doses of systemic corticosteroids, antibiotics, and/or emergency treatment or hospitalization. Adverse events will be reported quarterly to the independent safety officer for review, and will also be reported annually for IRB continuing reviews and NIH progress reports.

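### Section 10 lists no physical risk although half the sample is assigned a walking programme without professional supervision, and no structured prompt for physical events during activity is described

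*Combined protocol and SAP*

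**What the plan says.** Section 10.0 (Risks to Participants) calls the study minimal risk and says: "Potential risks include psychological distress and loss of confidentiality". It then explains the two in turn, one from answering private questions and one from data handling. Physical activity appears there only as a topic participants report on. Remote conduct is credited with removing the risks of in-person visits. Section 11.0 goes on to judge the risk/benefit ratio highly favourable.

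Section 4.0 (Intervention components) describes ground-based walking training as allowing "light to moderate intensity physical activity without the need for specialized equipment or professional supervision". Participants assigned to it receive a pedometer, a booklet for setting up a walking programme, and three brief calls over 6 weeks to review step counts and set personal activity goals. The same paragraph describes the programme as safe and well established.

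Section 15.0 (Monitoring of Safety Data) defines an adverse event broadly: any unfavourable medical event, symptoms included, whether or not related to participation. Staff ask for all such events since the last contact at mid-treatment, end-of-treatment and 90-day follow-up, and participants may report one at any time. The only event named is in the sentence that begins "Adverse events to be assessed include COPD exacerbation". Serious events go to the safety officer and the IRB within 24 hours, whatever their relation to the study. Table 2 lists adverse events as a measure at every timepoint, but the form itself is not reproduced.

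**The concern.** Walking training is the one component that asks participants for regular physical exertion. They are adults aged 40 or over with self-reported COPD who can walk at least one block unaided (Section 3.0). The risk section does not mention that exertion, so the weighing in Section 11.0 is made without it.

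The second issue is measurement. The stated method is an open question with one example, exacerbation. A stumble, a sore knee or breathlessness on a walk may not strike a participant as something to report. Walking participants also speak to staff more often than the others, so they have more occasions to mention such things. If adverse events are later compared by walking ON/OFF, a difference could reflect either harm or opportunity to report.

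This matters more than usual in a pilot whose purpose is to settle procedures for a full optimization trial, because the method of collecting events is likely to be carried forward. The Analytic Strategy in Section 4.0 has three areas, and none of them mentions tabulating adverse events.

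**Working it through.** **1. How many are assigned walking.** Section 4.0 states: "This will result in a total of 16 study conditions, 3 participants per condition (N=48"). Check: 2 x 2 x 2 x 2 = 16 conditions, and 16 x 3 = 48, which agrees with "The randomized factorial experiment will consist of 48 participants". Table 1 has walking ON in conditions 1 to 4 and 9 to 12, that is 8 of 16. So 8 x 3 = 24 of 48, or 50%, are assigned walking under the planned allocation.

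**2. Risks against components.**

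| Source | Content | Physical exertion covered? |
|---|---|---|
| Section 10.0, first risk | Distress from self-report | No |
| Section 10.0, second risk | Loss of confidentiality | No |
| Section 10.0, remote conduct | Removes risks of in-person visits | No; the walking takes place away from the study site |
| Section 11.0 | Risk/benefit judged favourable | Relies on the list above |
| Section 4.0, walking training | Activity goals over 6 weeks, "without the need for specialized equipment or professional supervision" | This is the exertion |

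**3. How events are elicited.** There are three scheduled inquiries: Week 5, Week 8 and Week 14. The recall windows are 5 - 0 = 5, 8 - 5 = 3 and 14 - 8 = 6 weeks. The question is open and the definition wide. The text gives one named event and describes no fixed item on falls, injury or symptoms during activity.

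**4. Contacts by walking level.** Section 4.0 gives two or five education calls, two inhaler sessions if ON, and three walking calls if ON. The two caregiver calls go to the caregiver and are left out. Because the factorial is balanced, the other factors average out equally across walking ON and OFF:

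- Education: (2 + 5)/2 = 3.5 calls on average.
- Inhaler: (2 + 0)/2 = 1 session on average.
- Walking OFF: 3.5 + 1 = 4.5 treatment contacts.
- Walking ON: 4.5 + 3 = 7.5 treatment contacts.

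With the three scheduled adverse-event inquiries added, the totals are 7.5 (OFF) and 10.5 (ON). The walking calls are not described as collecting adverse events. They are occasions to volunteer one.

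**5. What 24 participants can show.** The documents give no rate for walking-related events, so the rates p below are assumptions. With complete capture, P(at least one event) = 1 - (1 - p)^24:

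- p = 2%: 1 - 0.98^24 = 38%
- p = 5%: 1 - 0.95^24 = 71%
- p = 10%: 1 - 0.90^24 = 92%

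If none is seen, the one-sided 95% upper bound solves (1 - p)^24 = 0.05, so p = 1 - 0.05^(1/24) = 11.7%. Incomplete capture would make a report of no events less informative still. The documents give no capture fraction, so no figure is put on that loss.

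**The case against.** The strongest reply is that the plan already asks. Staff inquire about all adverse events at three contacts, under a definition that a fall, an injury or chest pain would meet. The word 'include' introduces an example, not a closed list. Participants can report at any time, and serious events are captured regardless of relatedness. Some of the 15 to 20 interviewed participants may also raise problems, because the interviews cover negative aspects of treatment. All of this stands. A reader might infer that nobody asks about physical harm, or that it goes unprompted. Section 15.0 does not support that. The gap is limited to non-serious events and to the absence of a described, specific prompt. Because the adverse-event form is not reproduced, it may already contain such items.

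A second reply is that Section 4.0 calls walking training safe and says goals follow exercise guidelines, so a minimal-risk label is consistent with it. That supports a low risk. It does not explain why the section listing risks leaves out the component altogether. How much weight the risk deserves is for the IRB.

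Two further inferences should be resisted. One is that participants are not told of the risk. The consent pages are not available for review, so that cannot be judged. The other is that Section 10.0 contradicts the Background, which says the framework can detect "unintended harmful effects (i.e., inappropriate management strategies for an exacerbation"). That example concerns managing exacerbations, not walking.

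Finally, the extra calls could be seen as a safeguard for walking participants. They may well be one, but they also leave reporting opportunity unequal between the levels being compared.

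**Conclusion.** The point holds in a limited form. Section 10.0 omits any physical risk from a component assigned by plan to 24 of 48 participants, and Section 11.0 relies on that list. Collection of adverse events is active and broad, but as described it has no structured prompt for physical events during activity, and walking ON carries three more staff contacts than OFF. Incomplete and unequal capture of non-serious events is therefore possible. The documents do not show that it would occur or how large it would be.

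This rests on the planned allocation, on the calls being delivered as described, and on the unseen adverse-event form having no such items already. The 11.7% bound assumes complete capture in all 24; the detection figures also depend on the assumed event rates. The point does not show that the walking programme is unsafe or that safety monitoring is absent. It is a worthwhile, inexpensive improvement, not a flaw that undermines the pilot.

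**What to change.** 1. Reconcile Section 10.0, and the risk/benefit statement in Section 11.0, with the walking component in Section 4.0, so that the three give one consistent account of physical risk. The wording is for the investigator and the IRB.
2. Add a few fixed items on falls, injury and symptoms during activity to the REDCap adverse-event questionnaire at Weeks 5, 8 and 14. Keep the open question. Word the items identically in all 16 conditions. If the form already has such items, say so in Section 15.0.
3. State in the Analytic Strategy that these events will be tabulated by walking ON/OFF, descriptively, with those found at the scheduled inquiries shown separately from those volunteered at other contacts.

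The cost is an IRB amendment, a small REDCap change, a slightly longer survey at existing contacts, and more minor events to log. Sample size, randomization and the delivery of any component are unchanged.
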